6.3.1.2 Supplementary and Sensitivity Analyses

Per Protocol Analysis

Additionally, the primary efficacy analysis will be repeated on the per protocol population (which excludes subjects with important protocol deviations that may affect the inference on efficacy such as a change in dose or type of concomitant AED medication).

Percentage Reduction from Baseline

The ANCOVA employed in the primary analysis uses log CSF_{T+M} as the response and adjusts for baseline seizure frequency by incorporating CSF_B as a factor in the model. The alternative approach described here calculates the percentage change in CSF from baseline directly and uses that quantity as the response variable in an ANCOVA model. Specifically, the ANCOVA will use the percentage change from the T+M period as the response variable, baseline CSF as a covariate, and treatment and age stratum as classification factors. A parametric ANCOVA will then be used to compare ZX008 treatment group to placebo treatment group.

If the distributional assumptions for the parametric analysis are not met, a nonparametric ANCOVA based on the ranks as the dependent response variable, and using the ranks of the baseline as covariate will be used for the analysis.

Criteria for Establishing Efficacy

While several supportive and/or supplementary analyses are specified above, the main criterion for demonstrating efficacy will be the primary analysis for the mITT population. It is conceivable that some or all of the supplemental analyses may not reach statistical significance. However, it is expected that the direction of effect will be consistent in favor of ZX008 versus Placebo.

6.3.2 Key Secondary Analyses

6.3.2.1 Proportion of subjects with ≥50% Reduction from Baseline in Convulsive Seizure Frequency (50% Responder Rate)

Subjects with a percent reduction in convulsive seizures of at least 50 percentage points from baseline will be identified and the overall proportion within each treatment tabulated. That is, the proportion of subjects in the ZX008 0.5 mg/kg/day group who have a decrease in convulsive

frequency of at least 50 percentage points will be compared to the analogous proportion in the placebo group.

The comparison between ZX800 treatment group and Placebo group will be made using a logistic regression model that incorporates the same factors as the ANCOVA used in the primary analysis. This will model a categorical response variable (achieved at least a 50 percentage point reduction, yes or no) as a function of treatment (ZX008 and placebo), baseline seizure frequency and age group (< 6 years, \geq 6 years).

Descriptive statistics will be presented by treatment group, and will include the number and proportion of subjects < 6 years, \geq 6 years, and overall achieving the reduction along with the model estimated odds ratio (including a 95% confidence interval) and p-value for comparison of ZX008 0.5 mg/kg/day to placebo.

6.3.2.2 Proportion of subjects with 0 or 1 Convulsive Seizures

The proportion of subjects with either 0 or 1 convulsive seizure will be identified, descriptive statistics will be presented by treatment group, and will include the number and proportion of subjects.

A Fisher's exact test will compare the proportion of subjects with a 100% reduction, and also with at most 1 convulsive seizure, in the ZX008 0.5 mg/kg/day to the analogous proportion in the placebo group.

6.3.2.3 Longest Convulsive Seizure-Free Interval

The longest interval between convulsive seizures will be analyzed.

For each subject, the longest interval between convulsive seizures will be calculated over the entire T+M period. This will be derived as the maximum of the number of days between consecutive convulsive seizures. The intervals between consecutive convulsive seizures will be calculated as below, after which the longest interval between convulsive seizures will be derived.

If a subject has two consecutive days of missing diary data, the end of the current seizure-free interval will be the first date of missing diary data, and a new one begun on the next date that diary data are available and no seizure occurs [In that case, for purpose of calculation of this variable, all intervening days, after the 2nd day, with missing diary data, will be assumed to have a convulsive seizure occurrence, until the first available date with non missing diary data.]

Let Date0 (=Day1) be the first day of treatment. If convulsive seizure occurs on five days having dates as Date1, Date2, Date3, Date4 and Date5, where

Date5>Date4>Date3>Date2>Date1 \geq Date0, and let LDT = Last date of treatment in the maintenance period, where LDT \geq Date5, then the time interval between convulsive seizures will be calculated as follows:

I1=Date2 - Date1

CONFIDENTIAL

Final 25 June 2018

I2=Date3 - Date2

I3=Date4 – Date3,

I4=Date5 – Date4.

For completeness, we calculate the time to the first seizure as

I0=Date1 – Date0,

and the time from the last seizure to end of treatment as

I5 = LDT – Date5.

Here the duration of the longest interval =Maximum (I0, I1, I2, I3, I4, I5).

If the subject does not experience a seizure during treatment, then the last available diary date will be used to compute the duration of the longest interval as follows:

The longest interval=last available diary date – Date0

The median time of the longest convulsive seizure-free interval will be presented. Additional summary statistics will be presented, including mean, minimum, maximum, the 25th and 75th percentiles, 95% confidence intervals on the difference in medians between groups (Hodges-Lehman estimator).

The Wilcoxon rank sum test will be used to test for differences between ZX800 and placebo, and the p-value from this test will be presented. Boxplots of the longest interval data will accompany all descriptive statistics and all data will be provided in a data listing.

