10.4.2 Cohort 2 Treatment Periods

Baseline Period

The Baseline Period covers the approximately 42-day span just prior to randomization and the start of treatment. The baseline frequency of convulsive seizures will be calculated from data collected during this period.

Titration Period

The Titration Period covers the time period during which subjects are titrated to the assigned randomized dose. It begins on the first day of treatment (Study Day 1) and concludes on Study Day 21. The Titration Period applies to all subjects including placebo recipients.

Maintenance Period

The Maintenance Period covers the 12 weeks following the end of the titration period.

Titration + Maintenance (T + M) Period

The T + M period combines the Titration and Maintenance periods. The T + M period is considered the treatment period.

Follow-up Period

The Follow-up Period begins immediately at the end of T + M period and extends through Visit 13 (Day 120).

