3.2 COHORT 2 STUDY TREATMENT

The study period of cohort 2 subjects comprises a Baseline period (6 weeks), a T+M period (15 weeks: (21 days for dose titration + 12 weeks maintenance), a Taper period or transition period, and a Post Dosing visit after study completion or early termination.

Upon completion of the Baseline Period, subjects who qualify for the study will be randomized (1:1) in a double-blind manner to receive ZX008 (0.5 mg/kg/day, 20 mg/day maximum) or placebo. Randomization will be stratified by age group (<6 years, \geq 6 years) to ensure balance across treatment arms, and initially it was hoped that at least 40% of subjects will be in each age group. The actual % of subjects in each stratum may be different from this goal. Subjects will be assigned a randomization number by the IVR/IWR system upon confirmation that the subject qualifies for enrollment in the Titration Period. All subjects will be titrated to their randomized dose during the Titration Period. Titration will occur in 3 steps starting with a 0.2 mg/kg/day dose of ZX008 (or placebo equivalent) on Study Days 1-7, increased to a dose of 0.4 mg/kg/day on Study Day 8-14, and then increased to a dose of 0.5 mg/kg/day on Study Days 15-21; the maximum daily dose at any point is 20 mg/day. The duration of the titration period will be 21 days.

There will be cardiac safety follow-up of 3 to 24 months after study drug discontinuation for early termination or for subjects who complete the study but do not enroll in the open-label extension study. These results will be presented elsewhere.

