- d: The Visit 8 ECHO must be performed any time between Study Day 40 and Study Day 54. The Visit 12 ECHO must be performed any time between Study Day 90 and Study Day 113; if a subject discontinues early from the study, the ECHO should be scheduled as soon as practical. If the Study Day 43 ECHO was completed ≤ 30 days prior to early termination, the Visit 12 ECHO will not be performed provided the parent/guardian agrees to bring the subject to the clinic for the cardiac follow-up visit.
- e: Females of child-bearing potential
- f: Plasma sample for PK assessment will be conducted prior to the dose at the Follow-up visit and 1, 2, and 4-6 hours after dose administration for Subjects continuing into the open-label extension trial.
- g: Plasma sample for assessment of background AED(s) will be conducted prior to the dose of AED(s) at Visits 3, 6, 8 and 12.
- h: Study drug/diary dispensed for the transition for subjects entering the open-label extension trial and for tapering for subjects exiting the study.
- i: Site personnel will review study medication dosing procedure (titration) with parent/caregiver.
- j: Study drug administration begins in the morning of Study Day 1.
- k: Only adverse events related to cardiac safety will be collected at this visit.
- l: Mandatory one time collection any time during or after screening and before Visit 10.

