6.1.6 Visit Windows

The following rules will be used to window data into treatment periods tabulations. For all by-visit tabulations, the nominal visit as recorded on the CRF will be used.

Double Blind Treatment Period	The Double-Blind Treatment Period start date is the date of first dose. The Double-Blind Treatment Period end date is the last date the patient was on study treatment. The Double-Blind Treatment Period includes time from first
-------------------------------	---

	treatment start date, which includes 21 days of Titration period, 12 weeks of Maintenance period and Taper/Transition period (14 days) - For subjects who discontinue early from the study, the double-blind treatment period end date will be the date at the early termination visit (Visit 12).
Titration Period	The Titration Period covers up to the first 21 days of treatment while subjects are titrated to their randomized dose. It begins on the first day of treatment (Study Day 1) and extends through Visit 6 (when the patient has reached their randomization dose). The Titration Period applies to all subjects including placebo recipients. If a subject withdraws from the study prior to treatment in the maintenance period, all safety assessments and events up to and including the date of study withdrawal will be tabulated in the titration period.
Maintenance Period	The Maintenance Period covers the 12 weeks following the end of the titration period. It begins on the date of Visit 6 + 1 day and extends through the end of study/early termination visit (Visit 12).
Titration +Maintenance Period (T+M)	The T+M period combines the Titration and Maintenance periods, beginning on the date of first treatment (Study Day 1) and extending to the end of the 12 week Maintenance Period. The primary efficacy endpoint is calculated based on data from the T+M period.
Taper/Transition Period	The Taper/Transition period consists of approximate 14- days starting from end of study/early termination visit (Visit 12) + 1 day. For patients who are not entering into the open-label extension study, patients will gradually be tapered off of study medication. Patients entering the open-label extension study will first enter the transition phase where all patients will be on a dose of 0.2mg/kg/day at the end of this phase. The end date of this period is considered to be the date recorded at Visit 13.

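### SAP 6.3.2.3 closes the longest convulsive seizure-free interval at two different dates: one is not limited to T+M, the other is undefined for a child who has a seizure and stops in Titration

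*SAP*

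**What the plan says.** **Window.** SAP 6.3.2.3 states that for each subject "the longest interval between convulsive seizures will be calculated over the entire T+M period". SAP 3.2 describes "a T+M period (15 weeks: (21 days for dose titration + 12 weeks maintenance").

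**Closing date, child with at least one seizure.** "let LDT = Last date of treatment in the maintenance period". The last of the intervals I0 to I5 is LDT minus the date of the last seizure, and the section requires LDT to be no earlier than that seizure. SAP 6.1.6 says of Maintenance: "It begins on the date of Visit 6 + 1 day and extends through the end of study/early termination visit (Visit 12").

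**Closing date, child without a seizure.** "If the subject does not experience a seizure during treatment, then the last available diary date will be used to compute the duration". The score is that date minus the first treatment day.

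**Missing diary days.** A rule stands ahead of both branches: "If a subject has two consecutive days of missing diary data, the end of the current seizure-free interval will be the first date of missing" entries. Missing days after the second count as seizure days until the diary resumes.

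**Diary after Visit 12.** Footnote h of the SAP schedule reads "Study drug/diary dispensed for the transition for subjects entering the open-label extension trial and for tapering for subjects exiting the study". The same schedule collects the diary at Visit 13 (Day 120), and Protocol 6.2.5.11 has seizure activity reviewed from it there.

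**Meaning of treatment.** Protocol 10.4.2: "The T + M period is considered the treatment period". SAP 6.1.6, by contrast, counts the 14-day taper or transition as part of the double-blind treatment period.

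**The concern.** The endpoint is described as a T+M quantity, but the two stated closing dates do not deliver that for every analysed child.

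- The no-seizure date can fall after Visit 12. Those days are off the randomized regimen: drug is being tapered, or the child is moving towards the extension. Placebo children entering the extension receive ZX008 during transition. Protocol Table 7 and SAP Table 4 differ on when that begins and must be reconciled, but both show active drug in Days 8-14. A placebo child's interval could therefore include days on active drug.
- The LDT date does not exist for a child who never reaches Maintenance. The mITT set requires only one dose and one week of diary data, so a child who has a seizure and stops in Titration can be analysed without a defined final interval.

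This is the third alpha-controlled test. The SAP also asks for the median, mean, minimum, maximum, quartiles, a confidence interval for the difference in medians, boxplots and a listing. If the rule stays open, a programmer has to choose the closing date for these children.

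**Working it through.** **1. The plan's own figure.** T+M = 21 + 12 × 7 = 105 days, and 105 / 7 = 15 weeks, as stated. T+M is Days 1-105, with Visit 12 on Day 106. The arm sizes used in step 5 also reproduce for a 40-point difference, two-sided 0.05 and 90% power: SD 55 gives 40 per arm (SAP 6.1.10) and SD 58 gives 45 (Protocol 10.1).

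**2. Seizure-free completer** (score = closing day − Day 1).

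| Closing date | Score |
|---|---|
| Day 105, last planned T+M day | 105 − 1 = 104 |
| Day 106, Visit 12 | 106 − 1 = 105 |
| Day 120, Visit 13 (literal formula) | 120 − 1 = 119 |

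The excess is 119 − 105 = 14 days (14/105 = 13%), or 15 days against 104. A seizure-free child who stops on day d and keeps the diary through a 14-day taper gains (d + 14 − 1) − (d − 1) = 14 days.

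**3. The two meanings of treatment.** Take a first convulsive seizure on Day 110.
- If treatment means T+M only, the child stays in the no-seizure branch. The score is 119 days, with the Day 110 seizure inside the interval.
- If treatment includes taper or transition, the child moves to the seizure branch. Then I0 = 110 − 1 = 109 and, with LDT at Day 106, the final interval is 106 − 110 = −4. This breaks the section's own condition that LDT is not earlier than the last seizure.

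Neither reading returns the T+M answer of 105.

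**4. Child with a seizure who stops in Titration.** Suppose one seizure on Day 2 and last dose on Day 20. I0 = 2 − 1 = 1. The final interval is LDT − Day 2, and LDT does not exist. Closed at Day 20 it would be 18. If a program took the maximum over the computable intervals, the score would be 1. The largest such loss is 21 − 1 = 20 days (last seizure Day 1, last dose Day 21).

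**5. Effect on the Step 3 Wilcoxon test.** A child with a seizure cannot exceed LDT minus Day 1. A seizure-free completer at 104 or 105 therefore already holds essentially the top rank, and 119 mostly just breaks ties. Ranks move mainly for early stoppers: up to +14 days without seizures, up to −20 days for Titration stoppers with seizures.

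Twelve scenarios were simulated, 600 runs each. The documents do not give the following inputs, so they are assumptions:
- baseline rates lognormal with median 14 per 28 days;
- 0-10% of children seizure-free;
- 2-10% stopping in Titration, and 8% of the rest stopping later;
- ZX008-to-placebo seizure-rate ratio 0.5 to 1.0;
- 40 or 45 per arm;
- an undefined final interval is dropped;
- the reference scoring closes completers at Day 105.

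| Quantity | Range over scenarios |
|---|---|
| Change in rejection rate | 0 to 4 percentage points |
| p<0.05 verdict changed, no-seizure branch alone | 0 to 5.7% of runs |
| p<0.05 verdict changed, both branches | 0.2 to 7.0% of runs |
| Shift in ZX008 median, no-seizure branch alone | 0.0 to 0.3 days |
| Shift in ZX008 mean, no-seizure branch alone | 0.3 to 1.6 days |

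The largest changes came with 10% seizure-free on ZX008, 10% stopping in Titration and a rate ratio of 0.7. At 40 per arm the rejection rate there was 49.0% with T+M scoring, 52.8% with the no-seizure branch taken literally and 51.0% with both.

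**The case against.** The strongest reply is that the section's opening sentence governs everything below it. Protocol 10.5.1.2 also specifies the whole T+M period, and the title of SAP Listing 16.2.6.3b ties the interval to T+M. On that view the no-seizure date naturally means the last diary date within T+M. This stands as evidence of intent. A reader might infer that the SAP has settled on scoring seizure-free children to Day 120, and the documents do not support that. They contain an explicit formula that conflicts with the stated window.

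Other stronger readings also fail:
- **Diary gaps ignored for seizure-free children.** The missing-days rule precedes both branches and makes no exception. Only the order of application is left unstated.
- **No end date for any Titration stopper.** A seizure-free one has the last diary date. The gap concerns only those with a seizure.
- **The SAP discards their final interval.** It does not say so. It describes that interval as running to the end of treatment, so the intent can be guessed, and dropping it is one possible programming outcome. The missing-days rule may also close some intervals once the diary stops.
- **Any value above 105 is an error.** Visit 12 has a ±4-day window and the SAP's T+M follows actual visits. A seizure-free child seen on Day 110 would validly score 109.
- **The start date is also wrong.** Day 1 is unaffected; both problems concern the closing date.

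Even so, the opening sentence cannot supply an LDT for a child who never entered Maintenance, and step 3 shows that neither definition of treatment repairs the no-seizure branch.

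**Conclusion.** The point holds as an internal contradiction plus one undefined case in an alpha-controlled endpoint, and it should be corrected. The literal no-seizure formula adds about 14 days (13%) for a completer. The undefined final interval puts up to 20 days at stake for a child who has a seizure and stops in Titration.

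A reader might infer that the Step 3 test is materially compromised. The calculations do not support that: seizure-free completers keep their ranks, and the verdict changed in about 0 to 7% of simulated trials. That range rests on assumed seizure-free, dropout and rate-ratio values, and on the final interval being dropped. The practical exposure is in individual values, means, maxima and boxplots, and in the ranks of the few early stoppers.

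**What to change.** In SAP 6.3.2.3:
- Define one closing date for every subject: the last non-missing diary date on or before Visit 12 or early termination (end of T+M), whichever period the child stopped in.
- Use it in place of both LDT and the no-seizure end date.
- Make the no-seizure branch depend on seizures during T+M rather than during treatment.
- Confirm that the two-consecutive-missing-days rule is applied before that branch.
- State that taper and transition diary days are not used for this endpoint.

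The cost is a short SAP revision and a few lines of derivation code, with no new data.
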